10.2.2 Primary Analysis(es)

The primary efficacy variable is the change from baseline in overall MLSI score. The primary time-point is 8 weeks.

GlaxoSmithKline Consumer Healthcare Confidential

Template Version Effective: 22-Jun-2017

Page 50 of 61

 GlaxoSmithKline	Document Name	003208076ClinicalProtocol.pdf	Document Identifier	Effective Date
	Type	Version		
	eldo_clinicalellbc	0.0. DIFFERENT MESSAGING CURRENT	090032d580fb904c	14-Aug-2017 09:06:22
	Reason For Issue	Auto Issue		

Potassium Nitrate / Sodium Fluoride

208078

Final 1.0 Clinical Protocol

The overall MLSI (AxI) for each subject is derived at a tooth site level first before averaging over all the teeth sites assessed. The change from baseline is derived from the individual sites first before calculating the average change across the sites assessed.

The change from baseline in overall MLSI will be analysed using analysis of covariance (ANCOVA) with treatment as a fixed effect and baseline overall MLSI as a covariate.

The assumption of normality and homogeneity of variance in the ANCOVA model will be investigated. Violation of this assumption will be overcome using a suitable data transformation or a non-parametric technique (eg Wilcoxon Rank Sum test or Van Elteren Test).

There are no comparisons for the primary objective as the main objective is to look at the rank order of the treatments in level of stain reduction after 8 weeks of treatment. This will be achieved via the adjusted means and confidence intervals for the means along with plots of MLSI over time. The hypothesis is that the test products will reduce stain to a greater extent than the reference products.

Two comparisons of interest will be done under secondary and exploratory objectives. These comparisons are: -

Test Product 1 vs Reference Product 1

Test Product 2 vs Reference Product 2.

Analyses at weeks 2 and 4 form part of the exploratory objectives.

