4.5 Analysis of Secondary Objectives

4.5.1 Efficacy

The hypothesis is that the test products will reduce stain to a similar or greater extent than the reference products.

Two comparisons of interest will be done under the secondary objectives. These comparisons are:-

Test Product 1 vs Reference Product 1

Test Product 2 vs Reference Product 2.

The change from baseline in overall MLSI at Week 8 will be analyzed using ANCOVA with treatment as a fixed effect and baseline overall MLSI as a covariate.

From the above ANCOVA model, treatment differences between groups (Test Product 1 vs Reference Product 1 and Test Product 2 vs Reference Product 2), 95% Cis and p-values, will be provided ([Table 14.2.2.2](#)).

The assumption of normality and homogeneity of variance in the ANCOVA model will be investigated. Violation of this assumption will be overcome using a suitable data transformation or a non-parametric technique (e.g. Wilcoxon Rank Sum test).

| | | | | |
|---|------------------|--|---------------------|----------------|
|  GlaxoSmithKline | Document Name | gsk-208078-reporting-and-analysis-plan.pdf | | |
| | Type | Version | Document Identifier | Effective Date |
| | elido_controlled | 0.1, CURRENT; Most-Recent; In Review | 090032d580f4eeeb | |
| | Reason For Issue | | | |

Potassium Nitrate / Sodium Fluoride

208078

Final Statistical Reporting and Analysis plan Amendment 21NOV2017

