Final Statistical Reporting and Analysis plan Amendment 21NOV2017

6 Abbreviation

| Abbreviation | Term |
|------------------|---|
| AE | adverse event |
| TEAE | treatment-emergent adverse event |
| ANCOVA | analysis of covariance |
| CI | confidence interval |
| ITT | intent-to-treat |
| KNO ₃ | potassium nitrate |
| NaF | sodium fluoride |
| STP | sodium tripolyphosphate |
| MedDRA | medical Dictionary for Regulatory Activities |
| MLSI | Macpherson modification of the Lobene Stain Index |
| OST | oral soft tissue |
| SAE | serious adverse event |
| SOC | system organ class |
| PT | preferred term |
| TPI | Turesky modification of the Quigley Hein Index |
| A | Area |
| I | Intensity |
| SD | standard deviation |
| Med | median |
| Min | minimum |
| Max | maximum |
| RLR | review listing requirement |
| BDRM | blinded data review meeting |
| SAS | statistical analysis system |
| GSK CH | GlaxoSmithKline Consumer Healthcare |
| POP | proof of principle |

GlaxoSmithKline Consumer Healthcare Confidential

Page 19 of 53

| | | | |
|------------------|--|---------------------|----------------|
| Document Name | gsk-208078-reporting-and-analysis-plan.pdf | | |
| Type | Version | Document Identifier | Effective Date |
| elido_controlled | 0.1, CURRENT; Most-Recent; In Review | 090032d580f4eeeb | |
| Reason For Issue | | | |

Potassium Nitrate / Sodium Fluoride

208078

Final Statistical Reporting and Analysis plan Amendment 21NOV2017

7 Attachment 1: List of Data Displays

Study 208078_List of Outputs.xlsx

| | | | |
|------------------|--|---------------------|----------------|
| Document Name | gsk-208078-reporting-and-analysis-plan.pdf | | |
| Type | Version | Document Identifier | Effective Date |
| elido controlled | 0.1; CURRENT; Most-Recent; In Review | 090032d580f4eeeb | |
| Reason For Issue | | | |

Potassium Nitrate / Sodium Fluoride

208078

Final Statistical Reporting and Analysis plan Amendment 21NOV2017

8 Appendix 1: Template for Tables, Figures and Listings

This is a guideline which will give the guidance of treatment labels that will be used for the table header and in the figures, listings and in the footnotes.

The treatment labels for the column heading will be as follow:

- Test Product 1
- Test Product 2
- Reference Product 1
- Reference Product 2

The treatment comparison will be in below order;

Test Product 1 Vs Test Product 2

Reference Product 1 Vs Reference Product 2

The below footnotes will be used for each outputs;

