Test Product 1: 5% KNO₃ / 0.2542% NaF dentifrice with 0.5% spherical silica (RDA~38)

Test Product 2: 5% KNO₃ / 0.2542% NaF dentifrice with 1% spherical silica and 5% STP (RDA~58)

Property of GSK Consumer Healthcare
Confidential

May not be used, divulged, published or otherwise disclosed
without the consent of GSK

Template Version Effective: 15-Jul-2017

Page 21 of 53

| | | | |
|------------------|--|---------------------|----------------|
| Document Name | gsk-208078-reporting-and-analysis-plan.pdf | | |
| Type | Version | Document Identifier | Effective Date |
| elido controlled | 0.1; CURRENT; Most-Recent; In Review | 090032d580f4eeeb | |
| Reason For Issue | | | |

Potassium Nitrate / Sodium Fluoride

208078

Final Statistical Reporting and Analysis plan Amendment 21NOV2017

Reference Product 1: Sensodyne Pronamel Daily Protection (RDA~36).

Reference Product 2: Sensodyne Extra Whitening (RDA~166).

GlaxoSmithKline Consumer Healthcare Confidential
Page 22 of 53

| | | | |
|------------------|--|---------------------|----------------|
| Document Name | gsk-208078-reporting-and-analysis-plan.pdf | | |
| Type | Version | Document Identifier | Effective Date |
| elido controlled | 0.1; CURRENT; Most-Recent; In Review | 090032d580f4eeeb | |
| Reason For Issue | | | |

Potassium Nitrate / Sodium Fluoride

208078

Final Statistical Reporting and Analysis plan Amendment 21NOV2017

Protocol 208078

Program Run Date: DDMMYYYY

Table 14.1.1
Subject Disposition
All Screened Subjects

Study Population: All Screened Subjects (N=xxx)

| | Test Product 1 N (%) | Test Product 2 N (%) | Reference Product 1 N (%) | Reference Product 2 N (%) | Overall N (%) |
|-----------------------------|-------------------------|-------------------------|------------------------------|------------------------------|------------------|
| TOTAL SUBJECTS SCREENED | | | | | xxx |
| SUBJECTS NOT RANDOMIZED | | | | | xxx (xx.x) |
| DID NOT MEET STUDY CRITERIA | | | | | xxx (xx.x) |
| ADVERSE EVENT | | | | | Xxx (xx.x) |
| LOST TO FOLLOW UP | | | | | xxx (xx.x) |
| PROTOCOL VIOLATION | | | | | Xxx (xx.x) |
| WITHDRAWAL OF CONSENT | | | | | Xxx (xx.x) |
| OTHER | | | | | Xxx (xx.x) |
| SUBJECTS RANDOMIZED | xxx | xxx | xxx | xxx | xxx |
| COMPLETED STUDY | xxx (xx.x) | xxx (xx.x) | xxx (xx.x) | xxx (xx.x) | xxx (xx.x) |
| DID NOT COMPLETE STUDY | xxx (xx.x) | xxx (xx.x) | xxx (xx.x) | xxx (xx.x) | xxx (xx.x) |

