| Reason For Issue | | | |

Potassium Nitrate / Sodium Fluoride

208078

Final Statistical Reporting and Analysis plan Amendment 21NOV2017

Protocol 208078

Program Run Date: DDMMYYYY

Table 14.2.2.2
Statistical Analysis of Overall Change Baseline in MLSI Score
Intent-to-Treat Population

Study Population: Intent-to-Treat Population (N=XX)

| Visit | Test Product 1 | Test Product 2 | Reference Product 1 | Reference Product 1 |
|--------|---------------------------------------|-----------------------|---------------------|---------------------|
| | (N=XX) | (N=XX) | (N=XX) | (N=XX) |
| WEEK 2 | ADJUSTED MEANS (SE) [1] | X.XX (X.XXX) | X.XX (X.XXX) | X.XX (X.XXX) |
| | 95 % CI [1] | (X.XX, X.XX) | (X.XX, X.XX) | (X.XX, X.XX) |
| | P-VALUE [1] | 0.XXXX | 0.XXXX | 0.XXXX |
| | COMPARISON | DIFFERENCE (SE) [1,2] | 95% CI [1] | P-VALUE [1] |
| | TEST PRODUCT 1 VS REFERENCE PRODUCT 1 | X.XX (X.XXX) | (X.XX, X.XX) | 0.XXXX |
| | TEST PRODUCT 2 VS REFERENCE PRODUCT 2 | X.XX (X.XXX) | (X.XX, X.XX) | 0.XXXX |
| WEEK 4 | SAME AS ABOVE | | | |

[1] From ANCOVA with treatment as factors and baseline overall MLSI score as a covariate

[2] Difference is first named treatment minus second named treatment such that a negative difference favours the first named treatment

Page x of y

PPD

Programming note: The same summary would be provided for the Week 8 also.

| | | | |
|------------------|--|---------------------|----------------|
| Document Name | gsk-208078-reporting-and-analysis-plan.pdf | | |
| Type | Version | Document Identifier | Effective Date |
| elido controlled | 0.1; CURRENT; Most-Recent; In Review | 090032d580f4eeeb | |
| Reason For Issue | | | |

Potassium Nitrate / Sodium Fluoride

208078

Final Statistical Reporting and Analysis plan Amendment 21NOV2017

Protocol 208078

PROGRAM RUN DATE: DDMMYYYY

Table 14.2.6.1
Summary of TPI Score
Intent-to-Treat Population

Study Population: Intent-to-Treat Population (N=XX)

| Visit | TimePoint | Test Product 1 (N=XX) | | Test Product 2 (N=XX) | | ----- | Overall (N=XX) |
|-------------------|-------------------|--------------------------|-----------------------------|--------------------------|-----------------------------|-------|-------------------|
| | | Observed Values | Change from Pre-brushing | Observed Values | Change from Pre-brushing | | |
| BASELINE | PRE- BRUSHING | N | XX | XX | XX | ----- | XX |
| | | MEAN | X.XX | X.XX | XX | ----- | X.XX |
| | | SD | X.XXX | X.XXX | XX | ----- | X.XXX |

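### Do the wrong comparison pairs and column headings in the SAP's table templates put the planned analysis in doubt?

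*SAP*

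**What the plan says.** Protocol 10.2.2 names two comparisons of interest, the second being "Test Product 2 vs Reference Product 2"; the first sets Test Product 1 against Reference Product 1. SAP Amendment 4.5.1 repeats them and says the ANCOVA will supply "treatment differences between groups (Test Product 1 vs Reference Product 1 and Test Product 2 vs Reference Product 2", with 95% confidence intervals and p-values, in Table 14.2.2.2.

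Section 8, Appendix 1 of the Amendment holds the table templates and describes itself as guidance on treatment labels. It introduces the labels with "The treatment labels for the column heading will be as follow" and lists Test Product 1, Test Product 2, Reference Product 1 and Reference Product 2. It then gives the comparisons as "Test Product 1 Vs Test Product 2" and "Reference Product 1 Vs Reference Product 2", and sets product footnotes for every output.

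The template for Table 14.2.2.2 is headed "Test Product 1 | Test Product 2 | Reference Product 1 | Reference Product 1", although its comparison rows are the planned ones, beginning "TEST PRODUCT 1 VS REFERENCE PRODUCT 1". Tables 14.2.6.2 and 14.3.1.1.1 repeat the heading fault. Table 14.1.3 is headed with RDA values of 58, 77, 80 and 120. The SAP of 5 October 2017 has the same pairs and the same four faulty headings, and Addendum 1 (1 February 2018) does not touch them.

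**The concern.** Table 14.2.2.2 carries the primary and secondary stain results. The primary objective has no formal comparison: it is a ranking read from the four adjusted means, which this table reports by column. If the template were followed to the letter, the adjusted mean for Reference Product 2 (RDA about 166) would appear under the name of Reference Product 1 (RDA about 36). Protocol Section 2 expects those two products to rank second and last, so confusing them would blur the ranking that the study is meant to show. Table 14.2.6.2 (plaque) and Table 14.3.1.1.1 (treatment-emergent adverse events) would have the same fault.

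The comparison lines at the head of the appendix, taken as instructions, would also call for test against test and reference against reference. Neither contrast is planned, and the two that are planned would be left out.

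**Working it through.** No statistical figure is at issue, so the check is to set the texts side by side and count.

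**Step 1: comparison pairs**

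| Source | First pair | Second pair |
|---|---|---|
| Protocol 10.2.2 | Test 1, Reference 1 | Test 2, Reference 2 |
| SAP Amendment 4.5.1 | Test 1, Reference 1 | Test 2, Reference 2 |
| Rows of Table 14.2.2.2 | Test 1, Reference 1 | Test 2, Reference 2 |
| Rows of Table 14.2.6.2 | Test 1, Reference 1 | Test 2, Reference 2 |
| Opening of Appendix 1 | Test 1, Test 2 | Reference 1, Reference 2 |

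Four sources agree and one differs, with 0 of its 2 pairs matching. The odd one out is the labelling guide. The sections that define the analysis and the templates a programmer would fill in all carry the planned pairs.

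**Step 2: headings in the Amendment templates that print all four products**

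| Table | Product columns | Correct? |
|---|---|---|
| 14.1.1 | Test 1, Test 2, Reference 1, Reference 2 | Yes |
| 14.1.2 | Test 1, Test 2, Reference 1, Reference 2 | Yes |
| 14.1.3 | RDA 58, 77, 80, 120 | No |
| 14.2.2.2 | Test 1, Test 2, Reference 1, Reference 1 | No |
| 14.2.6.2 | Test 1, Test 2, Reference 1, Reference 1 | No |
| 14.3.1.1.1 | Test 1, Test 2, Reference 1, Reference 1 | No |

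Four of six are wrong. Three more templates (14.1.4.1, 14.2.2.1, 14.2.6.1) abbreviate the product columns, and what they print is right. Counting them gives 4 of 6 + 3 = 9.

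The study's RDA values, in product order, are about 38, 58, 36 and 166. In Table 14.1.3 none stands in the right position, and only 58 belongs to a study product.

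**Step 3: could a duplicated heading mislead?**

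- *Stain and plaque tables.* Two columns with one name are a visible fault. The second comparison row names Reference Product 2, so the missing column is exposed. Adjusted means from an ANCOVA without interaction are all evaluated at the same covariate values, so

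  difference (Test 2 − Reference 2) = adjusted mean (Test 2) − adjusted mean (Reference 2).

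  Hence adjusted mean (Reference 2) = adjusted mean (Test 2) − printed difference. Unless the two reference means coincide, this identifies the column from the table itself. Addendum 1 also adds Figures 14.2.3 (stain) and 14.2.4 (plaque), which plot the same adjusted means with all four products footnoted correctly.
- *Adverse event table.* There is no comparison row here. Listing 16.2.7.1.1 gives every event in randomized subjects by named treatment group, so each column can be rebuilt. Table 14.1.1 shows Safety population counts under correct names, but this helps only if arm sizes differ. With 124 randomized, 124 / 4 = 31 per arm, so the counts may tie, and the listing is the firmer check.
- *Table 14.1.3.* It reports exclusions from populations only. The label list in the same appendix supplies the right headings.

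**The case for a change.** The best case for acting is that the faults survived an amendment and an addendum. The Amendment even added a correctly headed template (14.1.2) while leaving the four wrong ones. Because the primary result is a ranking read across columns, a heading fault in Table 14.2.2.2 is not trivial. SAP 4.6.1.2 also names further tables for which no template is printed. If they were built from the printed ones, the fault could spread. Correction would cost a few words.

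The facts stand. The repeated heading is unlikely to come from reading the PDF: it occurs in the same three templates in both SAP versions, although some value cells have evidently been lost in extraction.

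The consequence does not stand. The appendix cannot be followed to the letter, because it fixes the four correct labels and then breaks its own rule in the templates. A programmer has to resolve that, and the label list, the footnotes and SAP 4.5.1 all point the same way. Nor does a labelling guide that sets out an order of presentation override the section that specifies the analysis. The further tables are covered by the same label rule.

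**Conclusion.** The mismatches are genuine but clerical: 0 of 2 pairs in the appendix opening match the plan, and 4 of 6 four-product templates have faulty headings. Putting them right would leave the ANCOVA, the two planned contrasts, the populations and the sample size as they are, and no result or conclusion would differ. The planned analysis can be read without ambiguity from Protocol 10.2.2, SAP 4.5.1 and the templates' own comparison rows. No change to the plan follows.

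This rests on two assumptions. The first is that programmers treat SAP 4.5.1 as the specification and Appendix 1 as layout guidance, which is how the appendix describes itself. The second is that ordinary quality control of outputs would notice two columns with the same name. Addendum 1 shows that draft topline outputs were reviewed and that unsuitable displays were picked up there. Whether any finished table carried the wrong label cannot be told from these documents.
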